### 11.3.2. Epstein-Barr Virus-DNA measurements

Epstein-Barr Virus DNA (by RT-PCR) in serum will be measured at baseline and on Day 1 of all cycles. Results and change from baseline will be summarized by cycle for the safety population using descriptive statistics (sample size, mean, median, STDEV, minimum, and maximum values). A by-subject listing will be provided.

## 11.4. Vital Sign Measurements

For vital signs, a shift table from baseline to worst post-baseline will be displayed for temperature, systolic and diastolic blood pressure and pulse by normal range categories (low/normal/high). Normal ranges given in [Table 2](#) will be used to determine the categories low, normal and high. A by-subject listing will be provided.

**Table 2: Normal Ranges of Vital Sign Measurements**

Test	Normal Range (Unit)
Diastolic Blood Pressure	60, 90 (mmHg)
Systolic Blood Pressure	100, 140 (mmHg)
Pulse	60, 100 (beats per minute)
Temperature	[35, 38] (°C)

## 11.5. Physical Examination

Any findings from physical examination before the start of study drug will be documented as medical history on the medical history CRF page and any findings after the start of study drug will be documented as AEs on CRF. Therefore, there will be no separate analysis for physical examination.

## 11.6. Electrocardiograms

The 12-lead ECG overall investigator interpretation will be documented at screening and EOT visits.

The shift of overall interpretation ('normal', 'abnormal, not clinically significant' and 'abnormal, clinically significant') from baseline to the final evaluation on treatment will be displayed in cross-tabulations.

A by-subject listing of ECG data will be provided.

CELGENE PROPRIETARY INFORMATION

## 12. PHARMACOKINETICS ANALYSIS

### 12.1. Plasma concentrations

A by-subject listing of PK blood sample collection times, derived sampling time deviations, and azacitidine concentrations will be provided. Azacitidine plasma concentrations will be summarized using descriptive statistics (number of subjects, arithmetic mean, STDEV, minimum, median, maximum, percent coefficient of variation, geometric mean, and geometric percent coefficient of variation) for each dose level/cycle/day, if/when appropriate.

Concentrations that are below the limit of quantitation (BLQ) will be treated as zero for the computation of descriptive statistics. Missing concentrations and concentrations from blood samples collected more than  $\pm 10\%$  of nominal time will be omitted from the calculation of descriptive statistics.

Individual subject concentration-time data and mean concentration-time data for each dose level/cycle/day will be graphically presented on linear and semi-logarithmic scales.

### 12.2. Pharmacokinetic Parameters

Following single dose administration, predose samples that are BLQ or missing will be assigned a numerical value of zero for the calculation of PK parameters. Any anomalous concentration values observed at predose will be identified in the clinical study report. Pharmacokinetic parameters will be computed if the anomalous value is  $\leq 5\%$  of the maximum drug plasma concentration ( $C_{max}$ ). If the anomalous value is  $> 5\%$  of  $C_{max}$ , the computed PK parameters for the given subject will be excluded from the PK descriptive statistics.

Any other BLQ concentrations will be assigned a value of zero if they precede quantifiable samples in the initial portion of the profile. A BLQ value that occurs between quantifiable data points, especially prior to  $C_{max}$ , will be evaluated to determine if reanalysis or exclusion of the data is warranted. Following  $C_{max}$ , BLQ values embedded between 2 quantifiable data points will be treated as missing when calculating PK parameters. Below the limit of quantitation values occurring at the end of the collection interval (after the last quantifiable concentration) will be treated as missing data. If consecutive BLQ concentrations are followed by quantifiable concentrations in the terminal portion of the concentration curve, these quantified values will be excluded from the PK analysis by assigning them a value of missing, unless otherwise warranted by the concentration-time profile. For the purpose of analysis, these trailing BLQ values may be designated as zero in the dataset if the PK program used to do the analysis (such as WinNonlin®) will treat trailing zero values as missing when calculating PK parameters.

Actual sampling times will be used in the calculations of pharmacokinetic parameters, which will be derived using noncompartmental methods with PhoenixTM WinNonlin® Professional Version 6.3, or higher, [redacted]. Graphics may be prepared with SAS Version 9.2, or higher; or Excel 2007, or higher; PhoenixTM WinNonlin® Professional 6.3, or higher; or S-Plus 8.2., or higher [redacted]

The following PK parameters will be calculated for azacitidine:

$AUC_{0-\infty}$	Area under the plasma concentration-time curve from Time 0 extrapolated to infinity, calculated as $[AUC_t + Ct/\lambda_z]$ . $C_t$ is the last quantifiable concentration. No AUC extrapolation will be performed with unreliable $\lambda_z$ . If AUC %Extrap is $\geq 25\%$ , $AUC_{\text{inf}}$ will not be reported
$AUC_{0-t}$	Area under the plasma concentration-time curve from Time 0 to the time of the last quantifiable concentration, calculated by linear trapezoidal method when concentrations are increasing and the logarithmic trapezoidal method when concentrations are decreasing.
$C_{\text{max}}$	Maximum observed plasma concentration, obtained directly from the observed concentration vs. time data.
$T_{\text{max}}$	Time to $C_{\text{max}}$ , obtained directly from the observed concentration versus time data.
$t_{1/2}$	Terminal phase half-life in plasma, calculated as $[(\ln 2)/\lambda_z]$ . $t_{1/2}$ will only be calculated when a reliable estimate for $\lambda_z$ can be obtained.
$CL/F$	Apparent total clearance, calculated as $[\text{dose}/AUC_{\text{inf}}]$ .
$V_z/F$	Apparent volume of distribution, calculated as $[(CL/F)/\lambda_z]$ .

The following PK parameters for azacitidine will be calculated for diagnostic purposes and listed, but they will not be summarized:

$\lambda_z$	Apparent terminal rate constant, calculated by linear regression of the terminal portion of the log-concentration versus time curve in plasma. Visual assessment will be used to identify the terminal linear phase of the concentration versus time profile. A minimum of 3 data points will be used for calculation.
	$\lambda_z$ will not be estimated if the terminal phase of the log-concentration versus time profile does not exhibit a linear decline phase, or if the regression coefficient $< 0.8$ .
$\lambda_z$ lower	Lower limit of time (hours) included in the calculation of $\lambda_z$ .
$\lambda_z$ N	Number of data points used in the calculation of $\lambda_z$ .
$\lambda_z$ upper	Upper limit of time (hours) included in the calculation of $\lambda_z$ .
Rsq	Regression coefficient for calculation of $\lambda_z$ .
%AUC Extrap	Percentage of $AUC_{\infty}$ due to extrapolation from the last quantifiable time point to infinity.

### 12.3. Pharmacokinetic Analyses

A by-subject listing of PK parameters will be provided. The PK parameters will also be summarized using descriptive statistics (number of subjects, arithmetic mean, STDEV, minimum, median, maximum, percent coefficient of variation, geometric mean, and geometric percent coefficient of variation) for each dose level/cycle/day. Also, when appropriate, graphical representations (egscatter plots, box plots) may be used to visualize the results.

### **13. BIOMARKER AND CORRELATION ANALYSES**

No biomarker and correlation analysis will be done due to limited tumor biopsy data collected.

CELGENE PROPRIETARY INFORMATION

#### **14.      QUALITY OF LIFE ANALYSIS**

Not applicable for this study.

CELGENE PROPRIETARY INFORMATION

## 15. INTERIM ANALYSIS

One interim analysis will be performed for Stage 1 according to Simon's optimal two-stage design based on efficacy evaluable population.

The ORR will be monitored by Celgene study team according to Simon's optimal two-stage design based on the efficacy evaluable population. The interim analysis will be performed using the data collected by the cutoff date for the interim analysis. The cutoff date is defined as the date when there are more than 4 responders observed in Stage 1 of Simon's two-stage design. If at Stage 1 the predefined activity is met ( $> 4$  responses [CR or PR] out of the first 17 efficacy evaluable subjects based on independent radiological assessment), then the study will continue to enroll an additional 34 subjects. If  $\leq 4$  responses out of 17 are observed, then the study enrollment will be stopped. All subjects enrolled prior to the cutoff date will be included in the interim analysis and all data up to the cutoff date will be summarized or listed.

The following summary tables and listings will be provided for the Stage 1 interim analysis:

- Analysis populations
- Demographic and baseline characteristics for the enrolled population
- Cancer history for the enrolled population
- ORR based on independent radiology assessment for the efficacy evaluable population
- ORR based on investigator assessment for the efficacy evaluable population
- Treatment exposure and dose modification for the safety population
- Incidence of TEAEs by MedDRA SOC and PT for the safety population
- Incidence of TEAEs leading to dose discontinuation for the safety population
- Incidence of TEAEs with outcome of death for the safety population
- Incidence of Grade 3 or 4 TEAEs by MedDRA SOC and PT for the safety population
- Incidence of serious TEAEs by MedDRA SOC and PT for the safety population
- Incidence of TEAEs of Special Interest by MedDRA SOC and PT for the safety population

- Listing of subject eligibility
- Listing of demographics and baseline characteristics
- Listing of cancer history
- Listing of dosing
- Listing of tumor assessment
- Listing of tumor response
- Listing of adverse events
- Listing of deaths
- PK and biomarker analysis provided there are sufficient data

The above related data for the Stage 1 interim analysis will be cleaned and the detailed data cleaning plan will be documented in the data management plan.

CELGENE PROPRIETARY INFORMATION

**16. CHANGES TO THE STATISTICAL ANALYSES SECTION OF  
THE PROTOCOL**

‘Enrolled Population’ is defined in SAP.

CELGENE PROPRIETARY INFORMATION

## 18. APPENDICES

### 18.1. Study schematic

### 18.2. Handling of Dates

Dates will be stored as numeric variables in the SAS analysis files and reported in DDMMYY format (eg, the Date9. datetime format in SAS). Dates in the clinical database are classified into the categories of procedure dates, log dates, milestone dates, outcome dates, and special dates.

- **Procedure Dates** are the dates on which given protocol-specified procedure are performed. They include the dates of laboratory testing, physical examinations, tumor scans, etc. They should be present whenever data for a protocol-specified procedure are present and should only be missing when a procedure are marked as NOT DONE (ND) in the database. Procedure dates will not be imputed.
- **Log Dates** are dates recorded in the CRF data logs. Specifically, they are the start and end dates for AEs and concomitant medications/procedures. They should not be missing unless an event or medication is marked as *ongoing* in the database. Otherwise, incomplete log dates will be imputed according to the rules in Appendix

17.2 (eg, for duration or cycle assignment). However, in listings log dates will be shown as recorded without imputation.

- **Milestone Dates** are dates of protocol milestones such as randomization, study drug start date, study drug termination date, study closure date, etc. They should not be missing if the milestone occurs for a subject. They will not be imputed.
- **Outcome Dates** are dates corresponding to study endpoints such as survival and disease progression. In most cases they are derived either from a milestone (e.g., the survival date is derived from the death date), or a procedure date (e.g., the disease progression date is derived from the date of the tumor scan that was used to determine disease progression). They may be subject to endpoint-specific censoring rules if the outcome did not occur, but are not otherwise subject to imputation.
- **Special Dates** cannot be classified in any of the above categories and they include the date of birth. They may be subject to variable-specific censoring and imputation rules.

Dates recorded in comment fields will not be imputed or reported in any specific format.

### 18.3. Date Imputation Guideline

#### 18.3.1. Impute Missing Adverse Events/ Prior or Concomitant Medications/Procedures

##### Incomplete Start Date:

*Missing day and month*

- If the year is the **same** as the year of the first dosing date, then the day and month of the first dosing date will be assigned to the missing fields.
- If the year is **prior to** the year of first dosing date, then December 31 will be assigned to the missing fields.
- If the year is **after** the year of first dosing, then January 1 will be assigned to the missing fields.

*Missing day only*

- If the month and year are the **same** as the year and month of first dosing date, then the first dosing date will be assigned to the missing day.
- If either the year of the partial date is **before** the year of the first dosing date or the years of the partial date and the first dosing date are the same but the month of partial date is **before** the month of the first dosing date, then the last day of the month will be assigned to the missing day.
- If either the year of the partial date is **after** the year of the first dosing date or the years of the partial date and the first dose date are the same but the month of partial date is **after** the month of the first dosing date, then the first day of the month will be assigned to the missing day.
- If the stop date is not missing, and the imputed start date is after the stop date, the start date will be imputed by the stop date.

*Missing day, month, and year*

- No imputation is needed, the corresponding AE will be included as TEAE.

**Incomplete Stop Date:** If the imputed stop date is before the start date, then the imputed stop date will be equal to the start date.

*Missing day and month*

- If the year of the incomplete stop date is the **same** as the year of the last dosing date, then the day and month of the last dosing date will be assigned to the missing fields.
- If the year of the incomplete stop date is **prior to** the year of the last dosing date or prior to the year of the first dosing date, then December 31 will be assigned to the missing fields.
- If the year of the incomplete stop date is **prior to** the year of the last dosing date but is the same as the year of the first dosing date, then the first dosing date will be assigned to the missing date.
- If the year of the incomplete stop date is **after** the year of the last dosing date, then January 1 will be assigned to the missing fields.

*Missing day only*

- If the month and year of the incomplete stop date are the **same** as the month and year of the last dosing date, then the day of the last dosing date will be assigned to the missing day.
- If either the year of the partial date is **not equal to** the year of the last dosing date or the years of the partial date and the last dosing date are the same but the month of partial date is **not equal to** the month of the last dosing date, then the last day of the month will be assigned to the missing day.

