**End of Treatment (EOT) Evaluation:** An EOT evaluation should be performed for subjects who are withdrawn from treatment for any reason as soon as possible after the decision to permanently discontinue treatment has been made. Radiologic response assessment will be repeated only if required per the defined study imaging schedule.

**Adverse Event (AE) Collection and Follow-up:** Any AE that started after signing ICF and up to 28 days after the last dose of IP and those serious AEs (SAEs) made known to the Investigator at any time thereafter that are suspected of being related to IP will be collected.

**Follow-up for Efficacy Endpoints:** All subjects who discontinue treatment for reasons other than disease progression, start of new anticancer therapy, or withdrawal of consent from the entire study will be followed for tumor response assessments and subsequent anticancer therapies.

**Follow-up for Survival:** After the EOT visit, all subjects will be followed every 8 weeks ( $\pm$  5 days) for survival until withdrawal of consent, death, or lost-to-follow up, whichever occurs first. Subsequent anticancer therapies should be collected at the same schedule. New anticancer therapy includes (but is not limited to) any systemic or local medication, surgery, radiation, or any other therapy intended to treat the subject's cancer.

Survival follow-up may be conducted by record review (including public records) and/or telephone contact with the subject, family, or the subject's treating physician.

**Pharmacokinetics:** A subset of enrolled subjects (Asian-Pacific island ethnicity only) at a selected number of experienced sites that have the ability to collect, process, and ship CC-486 PK samples will participate in PK sample collection. Six subjects of Asian-Pacific island ethnicity initially being administered 200 mg CC-486 on Days 1 to 14 of a 21-day cycle will be asked to participate in the PK sample collection at these selected sites. An additional 6 subjects of Asian-Pacific ethnicity will participate in the PK sampling if the dose is escalated to 300 mg in this population.

On each PK day (ie, Cycle 1 Days 1 and 14), subjects will ingest IP in the clinic after performing the required overnight fasting, if applicable taking antiemetic premedication (eg, odansetron), and completing the required pre-dose assessments (where applicable), with each dose being given at approximately the same time of day.

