### 11.1. Adverse Events

Adverse events will be analyzed in terms of TEAEs which are defined as any AE that begins or worsens on or after the start of study drug through 28 days after the last dose of study drug. All AEs will be coded using MedDRA version 19 or higher.

A treatment-related TEAE is defined as a TEAE which was reported as “Suspected” on the CRF. Adverse events with a missing relationship will be treated as “treatment-related.”

The incidence of TEAE will be summarized by MedDRA SOC and PT. Severity of AEs will be graded 1 to 5 according to the CTCAE Version 4.0 or higher. For all other AEs not described in the CTCAE, severity will be assessed by the investigator as mild (Grade 1), moderate (Grade 2), severe (Grade 3), life-threatening (Grade 4) or death (Grade 5).

Tables summarizing the number and percentage of subjects experiencing TEAEs by treatment dose and for total safety population will be generated for each of the following:

- All TEAEs by SOC and PT
- All TEAEs by SOC
- All TEAEs by PT
- All TEAEs by Preferred term with Incidence of >5%
- All TEAEs by onset cycle
- Treatment-related TEAEs
- TEAEs of Grade 3 or 4
- Treatment-related TEAEs Grade 3 or 4
- All TEAEs by maximum CTCAE grade
- Treatment-related TEAEs by maximum CTCAE grade
- Serious TEAEs
- All serious TEAEs by Preferred term with Incidence of >5% Treatment-related serious TEAEs
- All treatment-related serious TEAEs by Preferred term with Incidence of >5%
- TEAEs with action of study drug withdrawn
- Treatment-related TEAEs with action of study drug withdrawn
- TEAEs with action of study drug dose reduced

- Treatment-related TEAEs with action of study drug dose reduced
- TEAEs with action of study drug dose interrupted
- Treatment-related TEAEs with action of study drug dose interrupted
- TEAEs with outcome of death
- Treatment-related TEAEs with outcome of death
- All deaths within 28 days of last dose with cause of death
- TEAEs for the following baseline subgroups (provided the number of subjects is sufficient):
  - Age (< 65 years, 65 years to < 75 years, ≥ 75 years)
  - Sex

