### **18.3.3. Adverse Events**

Partially missing AE start dates will be imputed in the derived dataset for AEs, but partially missing AE end dates will not be imputed in the same dataset. If the AE end date is complete with no missing year, month, or day, and the partially missing start date imputed by the rules below is after the AE end date, then the start date will be imputed by the AE end date.

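### An adverse event with no start date at all is always counted as treatment-emergent, even if its recorded stop date is before the first dose

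*SAP*

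**What the plan says.** Section 11.1 of the SAP defines a TEAE as "any AE that begins or worsens on or after the start of study drug through 28 days after the last dose of study drug". Section 4.1 (adverse event collection) starts the collection window earlier, at consent: "Any AE that started after signing ICF and up to 28 days after the last dose of IP". The same section allows up to 21 days between consent and the start of treatment, so events that arise and resolve before dosing can be in the database.

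Section 18.3.1 gives the rules for incomplete start dates. When day, month and year are all missing, it says: "No imputation is needed, the corresponding AE will be included as TEAE". The stop date is not mentioned.

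Two other provisions do use the stop date. One is in Section 18.3.1, listed under the heading for a missing day only, and applies where "the imputed start date is after the stop date, the start date will be imputed by the stop date". The other is in Section 18.3.3 and applies where "the partially missing start date imputed by the rules below is after the AE end date".

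**The concern.** The rule for a wholly missing start date is unconditional, whereas the definition it serves turns on timing relative to the first dose. A recorded stop date before the first dose settles that timing even when the onset is unknown, because the event was over before treatment began. The rule sets this information aside and classes the event as treatment-emergent.

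At stake is the correctness of the TEAE counts and their agreement with the listings. Section 18.2 says that listings show log dates as recorded. A reader could therefore find an event with a stop date before the first dose that the tables count as treatment-emergent. Section 11.1 also treats a missing relationship as treatment-related, so a record lacking both start date and relationship would enter the related-event tables as well.

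**Working it through.** The plan gives no figure to reproduce here. The check traces the rules for one type of record. Let D be the first dose date and S a complete recorded stop date.

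**Case A: start date wholly missing, S before D.**
- Section 11.1: an event that ended before D can neither begin nor worsen on or after D. Result: not a TEAE.
- Section 18.3.1, all three fields missing: included without condition. Result: TEAE.
- Stop-date check in 18.3.1: it acts on an imputed start date, and none is imputed here. It does not apply.
- Stop-date check in 18.3.3: it is limited to partially missing start dates. It does not apply.

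The two results conflict, and nothing else in the SAP resolves them.

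**Case B: start day missing, month and year equal to those of D, same S before D.**
- Section 18.3.1 first sets the start to D.
- D is later than S, so the stop-date check moves the start back to S.
- S is before D. Result: not a TEAE, in agreement with 11.1.

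**Case C: start day and month missing, year equal to that of D, same S before D.**
- Section 18.3.1 sets the start to D, and the check in 18.3.3 moves it back to S. Result: not a TEAE.

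**Case D: start date wholly missing, and the stop date is on or after D, missing, or the event is ongoing.**
- The timing of onset relative to D is unknown. Result under 18.3.1: TEAE, which is a sensible conservative default.

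Cases A, B and C carry the same evidence that the event was over before treatment. Only in case A is that evidence ignored, and only case A is misclassified.

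**Size.** Section 11 reports safety by dose for the Safety Population, and the SAP does not give the number in either column. Section 4.1 plans for the first 6 Asian-Pacific Island subjects evaluable for safety to receive 200 mg. If that column held exactly 6 (an assumption; the number dosed could be larger), one misclassified subject would change an incidence row by 1/6 = 16.7 percentage points. The number of affected records cannot be derived from the document.

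**The case against.** The strongest reply is that counting an event of unknown onset as treatment-emergent is a conventional conservative default. It can overstate toxicity but cannot hide it. That is sound for case D, and the default should stay there. It does not cover case A, where the timing relative to treatment is known.

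The second reply is rarity, and it stands. The record must lack the whole start date yet carry a stop date before the first dose. Section 18.2 expects adverse event dates to be present unless the event is ongoing, and an ongoing event has no stop date. Section 11.5 also sends physical examination findings made before study drug to medical history, which removes some pre-dose findings from the adverse event data.

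A reader might infer more than the text supports:

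- **That the event would enter every TEAE table.** It would not. Many tables in Section 11.1 are restricted by grade, seriousness, action taken, outcome or relationship. Without an onset date the event cannot be placed in the by-onset-cycle table, since Section 5.1 assigns cycles by date. A subject is also counted once per SOC or preferred term, so a row does not change if the same subject has the same term on treatment.
- **That it would usually be counted as treatment-related.** That needs a reported suspicion or a second missing field.
- **That the effect on the total column can be computed from the planned 17 to 55 subjects.** Those are efficacy-evaluable numbers. The safety tables use everyone who received a dose, including subjects replaced as not evaluable, and Section 10.2 states that the second stage was not entered.

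**Conclusion.** The point holds as a contradiction between two rules: Section 18.3.1 classes as treatment-emergent a record that Section 11.1 excludes, and it does so against the principle applied to partially missing start dates. It is a stated rule that misclassifies a definable record, not a detail left open.

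Its importance is minor. Such records should be rare and there may be none; nothing in the document shows that one exists. The error runs in one direction, towards over-counting TEAEs, and reaches only the tables whose criteria the event meets. ORR, PFS, DCR and OS are unaffected. The 16.7 points for one subject rests on an assumed 200 mg column of 6 and on a record that may never occur. It illustrates sensitivity in a small column and is not an expected bias.

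**What to change.** Amend the line in Section 18.3.1 for a start date missing day, month and year to read: *No imputation; the AE is included as a TEAE unless its stop date (complete, or partial but unambiguous) is before the first dose date.*

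A partial stop date should count as unambiguous only when its recorded fields alone place it before the first dose, for example a month and year earlier than the month of first dose. A stop date in the same month as the first dose with the day missing remains ambiguous, and the event stays a TEAE. Using the recorded fields also fits Section 18.3.3, under which partially missing adverse event end dates are not imputed.

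The cost is one clause in the SAP and one condition in the TEAE derivation. No new data are needed, and the conservative default is kept wherever the timing is truly unknown.
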